Appendix A

Visit 1 Case Report Form

Date / /
 dd mmm yyyy

Last dose of Parkinson's medications: _____ am / pm

Time DBS device turned off: _____ am / pm

To be completed by unblinded examiner

Subject randomization for initial DBS setting (Circle): Burst / Baseline

Left Right

Active Contacts

Amplitude

Pulse Width

Frequency _____

Subject Programming Preference (Circle): Burst / Baseline / No preference

Comments:

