- Unblinded examiner will then turn the DBS ON to the patient's baseline DBS settings continuously ON or to burst DBS mode (baseline DBS settings for the patient with DBS set to 1 sec ON, 4 sec OFF), based on results of randomization. The patient will be blinded to this programming change and will be kept at this initial setting for 30 minutes.
- Next, a blinded examiner who did not perform the programming change will perform a UPDRS-III evaluation. Next, the DBS will be turned off for 15 minutes to permit for a washout period.
- Next, the DBS will be turned on by the unblinded examiner to the alternate setting (burst DBS in case that the patient first was turned on with their baseline DBS setting or baseline DBS setting in case that the patient was first turned on with burst DBS setting) and kept on this setting for 30 minutes.
- After 30 minutes, the blinded examiner will perform another UPDRS-III evaluation. Patients, who are blinded to the stimulation setting, will be asked if they preferred one stimulation mode over the other.
- If any adverse events occur with burst DBS mode, the unblinded examiner will decrease the amplitude of the DBS by 0.5mA increments until the adverse events abate. If there are not persistent adverse events with 30 minutes of burst DBS mode, the patient will be kept in burst DBS mode at the end of first visit and will be allowed to take their Parkinson's disease medications.

Figure 1. Visit 1 Assessment Schema

Randomization Procedure

Subjects will be randomized to determine which DBS setting is initially programmed during visit one. All subjects will be programmed to both settings over the course of the visit, but the order is randomized to ensure appropriate blinding of the UPDRS assessor. Subjects have a 50% chance of being randomized to the “burst” mode, and a 50% chance of being randomized to the “baseline” mode. Following the initial UPDRS assessment (Meds OFF/DBS OFF), the study coordinator or unblinded assessor will use a computerized randomization system to determine which DBS setting the subject receives first.

Visit Two (6 months +/- 30 Days)

- Parkinson’s disease dopaminergic medications will be withdrawn overnight to establish medication-OFF state and DBS will be turned OFF overnight for establishing DBS-OFF state.

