- Examiner will establish a UPDRS-III baseline with medication-OFF, DBS-OFF state. Examiner will then turn the DBS ON to the burst DBS state and keep ON for 30 minutes. After 30 minutes the examiner will perform another UPDRS-III evaluation and will ask about any adverse effects. Patients will then be allowed to take their Parkinson’s disease medications and will be kept on the burst mode DBS state.
- Patients will be asked if they prefer the burst mode DBS state to their baseline settings before the study.

Visit Three (12 months +/- 30 days)

- Parkinson’s disease dopaminergic medications will be withdrawn overnight to establish medication-OFF state and DBS will be turned OFF overnight for establishing DBS-OFF state.
- Examiner will establish a UPDRS-III baseline with medication-OFF, DBS-OFF state. Examiner will then turn the DBS ON to the burst DBS state and keep ON for 30 minutes. After 30 minutes the examiner will perform another UPDRS-III evaluation and will ask about any adverse effects. Patients will then be allowed to take their Parkinson’s disease medications and will be kept on the burst mode DBS state.
- Patients will be asked if they prefer the burst mode DBS state to their baseline settings before the study. At the conclusion of the study, patients will be asked if they want to continue to use burst DBS state or if would prefer to be programmed back to their pre-study baseline DBS settings.

Phone Follow-Up Visits

Phone follow up calls will be completed by study personnel to determine subject’s programming preference at 1 week, 1, 3 and 9 months post programming changes.

Table 1. Schedule of Study Events

Activities	Screening/ Enrollment	Visit 1 (Baseline)	Visit 2 Month 6 +/- 30 days	Visit 3 Month 12 +/- 30 days	Phone Follow-up ⁴
Informed Consent	x				
Demographics	x				
Medical History	x				
Parkinson's Medications	x	x	x	x	x
Concomitant medications	x	x	x	x	x
Adverse Events		x	x	x	x
Serious Adverse Events		x	x	x	x
Adverse Device Effects		x	x	x	
UPDRS III (Meds OFF ¹ /DBS OFF ²)		x	x	x	
UPDRS III (Meds OFF ¹ /DBS ON- Burst)		x	x	x	
UPDRS III (Meds OFF ¹ /DBS ON- Baseline ³)		x			

¹ Parkinson's disease dopaminergic medications should be withdrawn overnight to establish medication-OFF state

² DBS should be turned off overnight to establish DBS-OFF state

³ DBS should be programmed to the baseline settings patient had before study entry

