Adverse event information will be collected throughout the study, beginning once the patient is enrolled in the study and monitored until each event is adequately resolved or explained. An AE or SAE description (including the nature of the event, date and time of onset, determination of non-serious versus serious, intensity, duration, causality, and outcome of the event) will be recorded on the case report forms by the investigator or research coordinator. A summary report of all serious adverse events will be provided to the reviewing IRB annually. Serious adverse events will be reported within 5 days of the investigator learning of the event to the reviewing IRB.

Secondary Endpoints

Burst DBS may require less energy and therefore a secondary endpoint we will include is a calculation of IPG (implanted pulse generator) or battery longevity. Secondary endpoints will also patient preference for stimulation mode.

Statistical Methods

Statistics will be performed using Mann-Whitney-U test and p-value < 0.05 will be required for statistical significance.

Regulatory and Ethical Considerations

Compliance Statement

This study will be conducted in full accordance all applicable Allegheny Health Network Research Policies and Procedures and all applicable Federal and state laws and regulations including 45 CFR 46, 21 CFR Parts 50, 54, 56, 312, 314 and 812 and the Good Clinical Practice: Consolidated Guideline approved by the International Conference on Harmonisation (ICH). All episodes of noncompliance will be documented.

The investigators will perform the study in accordance with this protocol, will obtain consent and assent, and will report unanticipated problems involving risks to subjects or others in accordance with the AHN IRB Policies IRB Policies and Procedures and all federal requirements. Collection, recording, and reporting of data will be accurate and will ensure the privacy, health, and welfare of research subjects during and after the study.

Risk Assessment

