Appendix A

Visit 2 and 3 Case Report Form

Subject # _____

Date / /
 dd mmm yyyy

Last dose of Parkinson's medications: _____ am / pm

Time DBS device turned off: _____ am / pm

Left Right

Active Contacts

Amplitude

—
—

Pulse Width

Frequency

Frequency _____

Frequency _____

Comments:

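### The only blinded preference answer is kept by mode name on the unblinded examiner's form, and a completers-only figure from the later, open-label answers risks favouring burst

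*Combined protocol and SAP*

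**What the plan says.** The Secondary Endpoints section states: "Secondary endpoints will also patient preference for stimulation mode". It gives no time point, does not say who asks, and has no rule for patients who leave.

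- **Visit One.** After both 30-minute periods, "Patients, who are blinded to the stimulation setting, will be asked if they preferred one stimulation mode over the other". The text does not say who puts the question. A blinded examiner has just done the second UPDRS-III rating.
- **Appendix A, Visit 1 form.** Under the heading "To be completed by unblinded examiner" come the randomised initial setting, the programming parameters and then "Subject Programming Preference (Circle): Burst / Baseline / No preference".
- **After Visit 1.** If no adverse events persist, "the patient will be kept in burst DBS mode at the end of first visit".
- **Visits Two and Three.** "Patients will be asked if they prefer the burst mode DBS state to their baseline settings before the study". Visit Three adds a choice between continuing burst and returning to the pre-study settings.
- **Phone Follow-Up Visits.** Calls establish "programming preference at 1 week, 1, 3 and 9 months post programming changes". No blinding is described.
- **Appendix A, "Visit 2 and 3 Case Report Form".** As shown, it has a comments line but no preference item.
- **Subject Replacement.** Subjects who cannot complete, with an adverse reaction to burst given as one example, are withdrawn and may be replaced so that five complete. Recruitment Strategy expects about 15 enrolled to give 5 evaluable.

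**The concern.** Preference is a subjective answer, so blinding matters more for it than for most endpoints. The plan obtains one blinded answer per patient but keeps it only after translation into a mode name, on the form of the person who knows the order. A blinded patient can say only that the first or second setting was better. That statement is not retained, so the translation cannot be audited.

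The later answers come from patients who know they are on burst and are comparing it with settings remembered from months before. Burst intolerance is a named reason for withdrawal and replacement, so the group still answering at 6 and 12 months may be selected for liking burst. If the published figure is the 12-month answer among five completers, it could overstate how many patients prefer burst. Nothing in the plan rules that choice out.

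**Working it through.** **1. Count the assessments.** Visit 1 (1) + phone calls (4) + Visits 2 and 3 (2) = 7, plus the continuation choice at the end. The patient is described as blinded at 1 of the 7.

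**2. Set the Visit 1 text beside the Visit 1 form.** The visit text keeps the patient blinded and words the question neutrally. The form offers only mode names, below the randomised order, under the unblinded examiner's heading. Someone must map period to mode at some stage. The gap is that the asker is unspecified and no first/second answer is kept before mapping.

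**3. Size of possible selection among completers.** The plan gives no preference figure to reproduce. Its only related figures are about 15 enrolled and 5 evaluable, an overall retention of 5/15 = 1/3.

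Let p be the true proportion preferring burst, and R the retention of those preferring burst divided by the retention of the others. R is an assumption, since the documents give no such figure. The expected proportion among completers is

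pR / (pR + 1 − p).

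Overall retention cancels, so the result does not depend on the 15.

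| True p | R = 1 | R = 2 | R = 3 | R = 5 |
|---|---|---|---|---|
| 30% | 30% | 46% | 56% | 68% |
| 50% | 50% | 67% | 75% | 83% |
| 70% | 70% | 82% | 88% | 92% |

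For example, with p = 0.5 and R = 2: 1.0 / (1.0 + 0.5) = 0.667. With R = 5: 2.5 / (2.5 + 0.5) = 0.833. At R = 1 there is no bias.

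**4. What this does to a result from five patients.** With q the expected completer proportion, the chance that at least 4 of 5 favour burst is 5q⁴(1 − q) + q⁵. For a true preference of 50%:

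- R = 1 (q = 0.50): 0.19
- R = 2 (q = 0.667): 0.46
- R = 3 (q = 0.75): 0.63
- R = 5 (q = 0.833): 0.80

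**5. Precision.** Even 5 of 5 gives a two-sided exact sign-test p of 2 × 0.5⁵ = 0.0625. With five patients the preference result is descriptive whatever the analysis, so who is counted determines what it says.

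**The case against.** The strongest reply is that none of this shows an actual bias, and much of it stands.

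- **Mode-name coding.** This does not change what a blinded patient says. An unblinded recorder can map first to burst or baseline without influencing the answer. A reader might infer from the form heading that the unblinded examiner asks the question. The documents do not say so, and the extracted page does not show how far down the form the heading applies. Any Visit 1 effect has no established direction.
- **Leaving versus stopping burst.** The Risk Assessment section lists stopping burst separately from exiting the study. A patient who dislikes burst may revert, stay in and still be asked. The early calls may also reach some patients before they leave. Subject Replacement names inability to attend visits as a reason too, so not every loss is about burst.
- **Missing form fields.** A reader might infer that later preferences have nowhere to be recorded. That holds only for the forms as shown. The Visit 2/3 form is broken by extraction and has a comments line, and neither form shows UPDRS-III scores, so other source forms may exist.
- **The extreme contrast.** A reader might set 5/5 = 100% of completers against 5/15 = 33% of those enrolled. That assumes all ten non-completers received burst and rejected it. Consent is taken at screening, so some may be lost before Visit 1. Recruitment Strategy also says recruitment stops at about 5 enrolled, so 15 is itself uncertain. Taken as bounds, 5/5 is compatible with anything from 5/15 = 33% to 15/15 = 100% of those enrolled.

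The reply does not supply a blinded record of the Visit 1 answer, or a rule for counting patients who give up burst.

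**Conclusion.** The point holds as a risk with an inexpensive remedy. Two protections are missing: a period-coded answer taken by the blinded examiner, and a preference figure that includes patients who stopped burst or left because of it.

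A reader might conclude that the plan biases the endpoint toward burst. The documents do not support that as a fact. The endpoint has no stated time point, selection bias is zero if retention does not depend on preference, and the direction of expectation effects in the open-label answers is not fixed. What they do support is that a completers-only figure could be inflated: from 50% to between 67% and 83% for assumed retention ratios of 2 to 5.

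Nor do they require the Visit 1 answer to be the sole endpoint. It is protected by blinding but rests on 30-minute exposures in the medication-OFF state. The later answers reflect longer use without blinding. Each has a weakness that the other lacks.

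**What to change.** 1. At Visit 1, the blinded examiner already present asks the question and records first, second or no preference before any unmasking. The answer is mapped to burst or baseline afterwards from the randomisation record, and the original answer is kept.
2. Report the blinded Visit 1 preference for every patient who completed both periods, including those later withdrawn or replaced.
3. Report later preferences separately, labelled open-label, for all patients who received burst. Count those who stopped burst or withdrew because of it as not preferring burst, and show losses for other reasons as a separate count.

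This needs a form edit and a short addition to the Secondary Endpoints section, with no extra staff, visits or change to treatment. The downside is a possibly less favourable preference figure. Because the Visit 1 answer reflects only brief exposures, both results should be shown.

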Appendix A

Visit 2 and 3 Case Report Form

Subject # _____

Date / /
 dd mmm yyyy

Last dose of Parkinson's medications: _____ am / pm

Time DBS device turned off: _____ am / pm

Left Right

Active Contacts

Amplitude

—
—

Pulse Width

Frequency

Frequency _____

Frequency _____

Comments:
